7.8 Rationale for the choice of the primary endpoint

In oncology clinical trials, *OS*, defined as the time from randomization until death due to any cause, is generally considered as the most convincing measure for drug efficacy and benefit and represents the gold standard primary endpoint for these trials ([FDA 2018](#)).

In the present observational study, the *time to medical treatment failure* (defined as the time from the start of treatment to the date of the following events, whichever comes first: subsequent systemic treatment, radiation therapy, mutilating surgery or death due to any cause), was chosen to be the primary endpoint.

The choice of the *time to medical treatment failure* as primary endpoint over *OS* was motivated by the results of recent studies ([Orbach 2020](#)) confirming the excellent *OS* of patients with IFS. A retrospective analysis performed in 2020 of all published data from patients with IFS of the European pediatric Soft tissue Sarcoma Study Group (EpSSG) and *Cooperative Weichteilsarkom Studiengruppe* (CWS) databases revealed that among the 172 European patients treated, 162 (94.2%) were alive at the end of the study follow-up. Among the 10 patients who died, 9 patients died because of the disease and one because of toxicity ([Orbach 2020](#)). Based on these observations, *OS* does not therefore represent the most relevant criterion to assess the therapeutic benefit of a treatment for IFS patients.

The challenges for IFS patients are the management of their morbidities and the long-term effects associated to the type of therapies used, which includes the resection of their tumor without anatomic and functional damage, as well as the administration of adapted therapies (alkylants, anthracyclines, radiotherapy) by minimizing acute and chronic toxicities, including minimal long-term consequences.

The retrospective analysis performed by Orbach et al. ([Orbach 2020](#)), showed that among the 172 patients included in the study, 65 patients (40% of all survivors) were treated with surgery alone and 64 (39%) with surgery combined with chemotherapy. Radiotherapy was delivered to 5 patients (3% of survivors), and 28 patients (17%) exclusively received chemotherapy. Among the 129 patients who were treated with surgery, 91% had conservative surgery (118 patients). Twenty patients (12%)

survived with major functional deficits or had mutilating surgery. In this series, almost 17% of patients may have experienced significant negative long-term effects with conventional therapies (20 patients treated with mutilating surgery and 5 with radiotherapy). In addition, 10 patients died mostly as a consequence of a tumor which was refractory to multiple lines of therapy. Altogether, these observations evidence that conventional conservative strategies demonstrate efficacy in IFS, even for the extensive tumors, but they are associated with acute and chronic side effects ([Orbach 2020](#), see [Section 7.4](#)).

To increase the robustness of the comparison for the primary analysis, events that are considered the most relevant in view of the multidisciplinary management of these tumor types will be selected. Chemotherapy is an essential component of the multimodality treatment with multiple lines considered in case of suboptimal outcomes, while surgery and radiation therapy acting as a local control may be associated with significant morbidities, with, in the worst case, failing to preserve the affected organ, particularly in the extremities. Three European studies analyzing the total burden of therapy for patients with IFS treated with conventional treatments showed that radiotherapy was used in 2.9% of patients, mutilating surgery was performed in 6.9% of patients and 5.2% of patients died of disease. Moreover, in main recent large series published in IFS, mutilating surgery, radiotherapy, alkylating chemotherapy and anthracycline agents were performed or used in 6-13%, 2-20%, 20-87% and 0-13% of cases, respectively ([Orbach 2020](#)).

The systemic treatment administered to the patient population targeted in this observational study is expected to either allow a complete response or to qualify the patient for non-mutilating complete surgical resection. Based on the experience of the experts of the field, tumor responses after conventional chemotherapy generally occur slowly over several months, whereas larotrectinib may lead to an early response (median time to response 1.8 months, with clinical improvement noted within days to weeks), which may be more important when there are life-threatening symptoms including tumor bleeding or organ compression. In cases of refractory tumors, life-threatening complications, or of metastatic tumors, TRKI should be immediately considered ([Orbach 2020](#)).

Events that constitute the primary endpoint (subsequent systemic treatment, radiation therapy, mutilating surgery or death due to any cause) were chosen based on the following rationales:

- They are all considered as markers of treatment failure from a clinical perspective and it is clinically relevant to avoid the occurrence of any of these events, because of associated morbidities and long-term toxicities:
 - Use of a subsequent treatment is considered when treatment response is not pronounced enough to qualify a patient for non-mutilating surgical resection or upon progression,
 - Radiation therapy is considered when systemic treatment fails as it can cause significant morbidity,
 - Mutilating surgery (at the investigator's discretion in SCOUT and external historical control cohorts): clinicians aim at avoiding mutilating surgery, it is the very last option in case of previous treatment failure to prevent evolution to the metastatic stage and associated risk of shortened survival,
 - Death.
- Measuring methods for those events in the SCOUT and external historical control cohort(s) seem more reliable than the evaluation of the PFS or tumor response, which are dependent upon local methods of reading radiological images.

- Due to the small patient population, the comparison with (an) external historical control cohort(s) and the anticipated rarity of events of clinical interest, the choice of a composite endpoint sounds the most appropriate approach.

8. Research questions and objectives

8.1 Primary objective

The aim of the study is to assess the therapeutic benefit of larotrectinib over the current standard of care in patients with locally advanced or metastatic IFS.

The primary objective of the present study is to compare the time to medical treatment failure (defined as: next systemic treatment or mutilating surgery or radiation therapy or death due to any cause) between larotrectinib and standard of care in IFS patients using externally-controlled comparison performed with phase I/II SCOUT study and eligible external historical cohort(s).

8.2 Secondary objectives

The secondary objectives in this study include the comparison of:

- Treatment outcomes (next systemic treatment, mutilating surgery, radiation therapy, death due to any cause),
- Treatment discontinuation rates due to toxicity.

9. Research methods

9.1 Study design

This study is a retrospective observational externally-controlled study. Data of patients with IFS in the eligible external historical cohort(s) will serve as control for the comparison with data of patients with IFS who have been enrolled in the SCOUT study. Data which will be used for the analyses will come from:

- SCOUT study:
 - At least 27 sites across 13 countries, including France.
- Eligible external historical control cohort(s) (see inclusion and exclusion criteria of databases in [Section 9.2.3.1](#)), including at least the *Institut Curie* database.

9.1.1 Primary endpoint

The primary endpoint of the study is the *time to medical treatment failure*: defined as the time (months) from the start of treatment to the date of the following events, whichever comes first: subsequent systemic treatment, radiation therapy, mutilating surgery or death due to any cause.

The rationale for the choice of this variable as primary endpoint, notably over OS variables is detailed in [Section 7.8](#).

9.1.2 Secondary endpoints

The secondary endpoints of the study are:

- Time to subsequent systemic treatment.
- Time to mutilating surgery including limb amputation.

- Time to radiation therapy.
- Time to complete surgical resection (excluding amputation).
- OS, defined as the time (months) from the start of treatment to the date of death due to any cause. Patients alive or lost to follow-up at the time of analysis will be censored at their last date of follow-up.
- Incidence of patients with treatment discontinuation due to treatment-related adverse events (AEs).

9.1.3 Exploratory endpoints

The following exploratory endpoints will also be investigated:

- Progression-free survival (PFS): defined as the time (months) from the start of treatment to the date of first observed disease progression (radiological or clinical, whichever is earlier; assessed by the treating physician in the external historical control cohort(s)) or death due to any cause, if death occurs before progression is documented. Patients without documented progression at the time of analysis will be censored at the date of last tumor assessment.
- Overall response rate (ORR): defined as the proportion of patients with a best overall response of complete response (CR) or partial response (PR), as assessed by investigators.
- Disease Control Rate (DCR): defined as the proportion of patients with a best overall response of CR, PR, or Stable Disease (SD).

9.2 Setting

9.2.1 Study population

The study population will comprise all patients of the SCOUT study and of the external historical control cohort(s) (including at least the *Institut Curie* database) with a diagnosis of locally advanced or metastatic IFS. Inclusion and exclusion criteria for patients are described in [Section 9.2.3.2](#).

9.2.2 Study time frame

This study, being a retrospective observational study, does not require diagnostic or therapeutic procedures nor the respect of a specific calendar for patient visits.

The detailed planned dates of the different milestones of the study are presented in Section 6 in [Table 1](#).

9.2.3 Selection criteria

9.2.3.1 Selection criteria for the sources of the external historical control cohort(s)

The choice of the external control cohort(s) to be included in the comparator arm is not arbitrary. In order to ensure a non-biased selection and to maximize as possible the sample size and power of the comparator group, the following actions were or will be undertaken:

- A comprehensive assessment of the existing databases in France and internationally will be performed from the following sources:
 - ✓ Databases found in the literature,

- ✓ Databases from clinical studies sponsored by Bayer or known by Bayer, notably through its interactions with experts in the field,
- ✓ Commercial databases with electronic medical data.
- A SLR will be conducted to ensure completeness of the identification of all databases that could be used as external historical control cohorts. This SLR will be based on a protocol of research including the following Patient, Intervention, Comparison, Outcome (PICO) criteria:
 - Population: IFS,
 - Intervention: N/A,
 - Comparison: N/A,
 - Type of studies: all interventional and observational studies except case reports,
 - Period: from 2000 to present,
 - Scope: international.

The SLR protocol and report will be annexed to the final study report.

The selection of data sources will be performed upon the following eligibility and feasibility criteria, with the following justifications:

- Inclusion criteria:
 - ✓ Cohorts with prospective enrollment and with retrospective and prospective data collection from 2000 to present.

This criterion was defined based on the following rationales:

 - The strong evolution of histological diagnostic in the 2000's,
 - The risk of classification bias if databases prior to 2000's were considered (e.g., with our current knowledge and the current classification, nowadays, some patients would not be diagnosed with IFS but with spindle cells rhabdomyosarcoma [[Orbach 2020](#)]),
 - The development and the use of biomolecular diagnostic since the 2000's: IFS diagnosis is no more considered in absence of *NTRK* gene fusion,
 - The absence of significant evolution in the IFS diagnosis and therapeutic approaches from 2000 to present: Chemotherapy (VA regimen) has been the standard of care for this indication for several decades (*reference: HAS opinion on larotrectinib*).
 - ✓ Cohorts containing at least clinical data allowing to assess the efficacy of the treatment and the main prognostic factors as follows:
 - Diagnosis and stage of the disease (locally advanced or metastatic),
 - Type of treatments (chemotherapy, radiotherapy, surgery: mutilating yes/no and date of the initiation or of the procedure,
 - Death and date,
 - Localization of the tumor (axis versus limb),
 - Size of the tumor (< 5 cm versus > 5 cm).
- Exclusion criteria:
 - ✓ Databases not containing patients with locally advanced or metastatic IFS,

- ✓ Medico-administrative databases or absence of data allowing the assessment of the efficacy of the treatment and main prognostic factors, or high rate of missing data (>10% on outcome and >25% on covariates),
 - The use of these databases, especially medico-administrative databases, is not feasible because of missing data and the limited information available on the clinical, biological, diagnostic and treatment data, notably for rare diseases like IFS. These limitations would be an issue for the prognostic, outcomes and selection criteria of patients.
- ✓ Cohorts with retrospective enrollment and case report,
 - Cohorts with retrospective enrollment or case report are subject to a greater risk of selection bias than those with prospective enrollment and with retrospective and prospective data collection, given that all patients who should have been considered to be included might have not been included a posteriori.
- ✓ Cohorts with prospective enrollment for which all patients were included before 2000,
 - There is a risk of classification bias for cohorts constituted before 2000 because of the evolution of the histological and molecular diagnosis of IFS (see details in the inclusion criteria).

Based on a preliminary search of databases and the selection criteria described above, in addition to the database of the *Institut Curie* which is the only database confirmed, the following data sources are theoretically eligible to be used to constitute (an) external historical control cohort(s) for the present study:

- Databases found in the literature (preliminary search that will be completed by the SLR):
 - ✓ Database from the European pediatric Soft tissue Sarcoma Study Group (EpSSG, a consortium housed in the University of Padua, Italy, European data),
 - ✓ Database from the *Cooperative Weichteilsarkom Studiengruppe* (CWS, Germany).
- Commercial databases with electronic medical data:
 - ✓ No eligible databases were found.

The comprehensive review of the literature (SLR) that will be performed might identify additional eligible cohorts. The availability, the access, and the feasibility of use of the different eligible databases identified will be then investigated. Further details will be described in the final study report.

9.2.3.2 Selection criteria for patients

- Inclusion criteria:

The inclusion criteria listed below are in line with those of the SCOUT study in terms of patients and disease characteristics:

- Age \leq 21 years old.
- Locally advanced or metastatic IFS.
- Patients with available information on clinical, radiological characteristics of their tumor, therapies administered and outcomes.
- Patients receiving larotrectinib in the SCOUT trial.

- Patients receiving at least chemotherapy-based regimen in the external historical control cohort(s).
- No opposition from the patients and/or representatives for data use.
- Exclusion criteria:
 - Patients treated with TRKi in the external historical control cohort(s).
 - Patients with documented absence of *NTRK* gene fusion:
 - Formal identification of *NTRK* gene fusion has not been retained as an inclusion criteria as the information might be missing from the databases used to constitute the external historical control cohort(s). Given the rarity of the condition and the anticipated small sample size, the study will authorize the inclusion of patients with unknown *NTRK* gene fusion status to maximize sample size while there is a limited risk of introducing a bias, as *NTRK* fusion is almost pathognomonic in IFS ([Orbach 2016](#)).
 - Patients participating in an investigational program with interventions outside of routine clinical practice.
- Population sampling strategy:

The study population will comprise all IFS patients in the SCOUT study and the eligible external historical cohort(s) (including at least the *Institut Curie* database) with a diagnosis of locally advanced or metastatic IFS regardless of their refractory or relapsed status, i.e. including treatment-naïve patients to avoid further reducing the sample size.

The choice of the study population has mainly been driven by feasibility/sample size considerations, in order to be able to perform a comparison based on a minimal number of patients.

In addition, the IFS population will also include patients with advanced or metastatic CMN since the histopathological characteristics of these tumors are very close to those of IFS, as mentioned in the WHO sarcomas classification ([Kallen and Hornick 2020](#)). Moreover, the presence of the same fusion transcript as in IFS is identified in the cellular form of CMN ([Thebaud 2012](#)).

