As a conclusion, in these various analysis, larotrectinib has demonstrated clinically meaningful antitumor activity in pediatric patients with locally advanced or metastatic solid tumors with *NTRK* gene fusions, including IFS, that had previously progressed and had little or no effective treatment alternatives and facing limb amputation or disfiguring surgery.

According to the European Society for Medical Oncology (ESMO) Scale of Clinical Actionability for molecular Targets (ESCAT), larotrectinib was classified as “tier I-C”, which is attributed “when clinical trials in multiple tumor types, or basket clinical trials, have demonstrated a clinically meaningful benefit for the target-drug pair with similar magnitude of benefit across the different tumor types” ([Mateo 2018](#)).

In the United States, FDA approved larotrectinib (Vitrakvi) in November 2018 with an accelerated approval in the following indication:

Vitrakvi is a kinase inhibitor indicated for the treatment of adult and pediatric patients with solid tumors that:

- have a neurotrophic receptor tyrosine kinase (NTRK) gene fusion without a known acquired resistance mutation,
- are metastatic or where surgical resection is likely to result in severe morbidity, and
- have no satisfactory alternative treatments or that have progressed following treatment.

In France, a Temporary Authorization of Use (*Autorisation Temporaire d'utilisation* [ATU]) was granted by the National Agency for Drug and Health Products Safety (*Agence Nationale de Sécurité du Medicament et des Produits de Santé* [ANSM]) in March 2019.

In September 2019, larotrectinib was granted a conditional MA in Europe, for the treatment of adult and pediatric patients with solid tumors that display a *NTRK* gene fusion:

- who have a disease that is locally advanced, metastatic or where surgical resection is likely to result in severe morbidity, and
- who have no satisfactory treatment options.

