9.2.4 Representativeness

Larotrectinib as monotherapy is indicated for the treatment of adult and pediatric patients with solid tumors that display a *NTRK* gene fusion,

- who have a disease that is locally advanced, metastatic or where surgical resection is likely to result in severe morbidity, and
- who have no satisfactory treatment options.

The positive opinion of the HAS for the conditional reimbursement of larotrectinib was given only for the pediatric patients with a diagnosis of locally advanced or metastatic IFS or another STS harboring an *NTRK* gene fusion, refractory or in relapse. Therefore, the data that will be used for the analyses of this observational study are data from IFS patients who are in line with the scope of the conditional reimbursement of larotrectinib, broaden to IFS regardless of their refractory or relapsed status, i.e. including treatment-naïve patients, in order to limit the further reduction of the sample size. Data will be extracted from the following sources:

- The SCOUT study, which is an international clinical trial conducted in 27 centers in 13 countries including France, started in December 2015,
- The *Institut Curie* database and the eligible databases identified through a SLR with an international scope according to the selection criteria described in [Section 9.2.3.1](#). The choice of using cohorts with prospective enrollment and with retrospective and prospective data collection from 2000 to present will avoid the risk of selection bias that could have occurred if cohorts with retrospective enrollment would have been included and the risk of classification bias if cohorts constituted before 2000 would have been included, notably because of the evolution of histological and molecular diagnosis of IFS in the 2000's. Therefore, the control cohort(s) that will be identified using this systematic approach with an international scope and the chosen selection criteria can be considered representative.

Even though the sample size is small (which is inherent to the very low incidence of the targeted indications), these sources can be considered as reliable and representative of the population targeted in the present observational study, given the time windows and the sources from which the data will be extracted (e.g. the *Institut Curie* database regroups data from French centers from all over the regions of France).

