9.7.1 Index Date and endpoints

The comparison of the two cohorts will be considered for the primary composite endpoint:

- Time-to-treatment-failure (earliest of next systemic therapy, radiotherapy, mutilating surgery or death due to any cause).

In addition, all secondary and exploratory endpoints detailed in [Section 9.1.2](#) and [Section 9.1.3](#) will be analyzed:

- Time to subsequent systemic treatment,
- Time to mutilating surgery or limb amputation,
- Time to radiation therapy,
- Time to complete surgical resection (excluding amputation),
- OS,
- PFS,
- Incidence of treatment discontinuation due to treatment-related AEs,
- ORR,
- DCR.

The analysis will include patients on both first and second line (or higher) therapy. For SCOUT patients, the index date will be defined as the start date of larotrectinib. For patients of the external historical control cohort(s), the index date will be the start date of the first line of chemotherapy. The initial imbalance on lines of therapy between treatment groups will be corrected in the statistical modeling, in particular the variable defined by time from locally advanced/metastatic disease to index date will be a key variable in the propensity score model. Given approximately 70% of SCOUT patients received larotrectinib as second line of treatment, while in the external historical control cohort(s) all patients will have received chemotherapy in first line of treatment, the proposed primary analysis is expected to provide a rather conservative estimate of treatment effect.

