6.2 Analysis of Primary Variable(s)

6.2.1 Primary Endpoint

The primary endpoint of the study is the time to medical treatment failure: defined as the time (months) from the start of treatment to the date of the earliest event from: subsequent systemic treatment, radiation therapy, mutilating surgery or death due to any cause.

The **index** date of the analysis of the primary endpoint will be defined as either the start date of larotrectinib treatment (for patients in the SCOUT study, regardless of line of therapy) or start date of chemotherapy (first line) for the external historical control cohorts. The end date is defined as the earliest of the following endpoints:

- Start date of a post-treatment systemic anti-cancer therapy, if any, or,
- Start date of a post-treatment radiation therapy, if any, or,
- Date of a post-treatment mutilating surgery, if any, or,
- Date of death due to any cause, if applicable.

Patients who do not record an event will be censored at the last known alive date.

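### The TRK-inhibitor exclusion for controls is not tied to the index date, so it can remove controls because they had a primary event

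*Protocol*

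**What the plan says.** - **Exclusion.** The protocol abstract and Protocol 9.2.3.2 exclude "Patients treated with TRKi in the external historical control cohort(s", without a time limit. The same list excludes patients in investigational programs outside routine practice, also without a time limit.
- **Time zero.** For controls, Protocol 9.7.1 states that "the index date will be the start date of the first line of chemotherapy". SAP 6.2.1 agrees.
- **Event.** The first component of the primary endpoint in SAP 6.2.1 is "Start date of a post-treatment systemic anti-cancer therapy, if any, or", with no exception for a TRKi. Protocol 7.8 explains why this counts as failure: "Use of a subsequent treatment is considered when treatment response is not pronounced enough to qualify a patient for non-mutilating surgical resection or upon progression".
- **Carry-forward.** SAP 5.1 admits a control to the full analysis set only if the eligibility criteria are met and chemotherapy was started. SAP 5.1.1 does not repeat the TRKi exclusion, but SAP 7 does not list it as dropped. Neither document gives the number of controls removed or a sensitivity analysis on the rule.
- **Calendar.** Protocol 9.2.3.1 admits "Cohorts with prospective enrollment and with retrospective and prospective data collection from 2000 to present". SCOUT "started in December 2015" (Protocol 9.2.4). Protocol 7.5.1 records a French temporary authorisation in March 2019 and then: "In September 2019, larotrectinib was granted a conditional MA in Europe".
- **Contrary statement.** Protocol 9.9, arguing that large imbalance is unlikely, says the study data contain no period in which both treatments could be had.

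**The concern.** An eligibility rule should use only what is known at time zero. This one uses what happens afterwards, and what happens afterwards is part of the primary endpoint. Controls must have started chemotherapy, so patients who received only a TRKi are already out. Apart from those given a TRKi before or together with their first chemotherapy, the rule can act only on patients who began chemotherapy and moved to a TRKi later. Every one of those has failed by the plan's own definition.

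Such patients are conceivable. The Curie patients were found through a genomics platform and all carry an NTRK fusion (Protocol 7.7 and 9.8), so they have the target that a TRKi requires. Protocol 7.8 reports that TRKi treatment is considered for refractory and metastatic tumours. Anyone removed would therefore tend to come from the poor-prognosis end, which is close to the refractory or relapsed population in the payer's reimbursement scope.

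With about eight control events expected, a handful of deletions would matter. The same selection would carry over to overall survival, to the other secondary endpoints and to the propensity weights.

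**Working it through.** **Step 1. The logic.** Let T be the TRKi start for a control and T0 the start of first-line chemotherapy.
- If T is before or at T0, exclusion is a proper baseline criterion.
- If T is after T0, the TRKi start is itself a subsequent systemic therapy. The primary event falls at T, or earlier if another component came first. The patient has an event with certainty and is removed.

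The text does not separate the two cases.

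**Step 2. Reproduce the plan's power (SAP section 4).** Inputs: 49 larotrectinib patients, 42 controls, pE = 0.04, pC = 0.19, hazard ratio (IRR) 0.25, two-sided alpha 0.05.

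Power = Φ( √(k·m)·|IRR − 1| / (k·IRR + 1) − 1.96 ), with k = n1/n2 and m = n1·pE + n2·pC.

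- k = 49/42 = 1.167
- m = 1.96 + 7.98 = 9.94
- √(1.167 × 9.94) × 0.75 / 1.292 = 1.977
- Power = Φ(1.977 − 1.960) = 50.7%, against a stated 51%

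With unlimited controls the formula gives 62.9% (stated 62.9%). With 35 larotrectinib patients and unlimited controls it gives 49.0% (stated 49%). The plan's figures reproduce.

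**Step 3. Put back x removed controls.** The documents do not give x, so the values below are assumptions and include zero. Each restored patient adds one patient and one event:

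pC(x) = (42 × 0.19 + x) / (42 + x)

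The last column shows the distortion if the drug had no effect. Both groups would then share the true risk pC(x), while the depleted controls would show 0.19, giving a crude risk ratio of pC(x)/0.19.

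| x | Control events / n | pC(x) | Power at HR 0.25 | Crude risk ratio under no effect |
|---|---|---|---|---|
| 0 | 7.98 / 42 | 0.190 | 50.7% | 1.00 |
| 1 | 8.98 / 43 | 0.209 | 54.0% | 1.10 |
| 3 | 10.98 / 45 | 0.244 | 60.0% | 1.28 |
| 5 | 12.98 / 47 | 0.276 | 65.1% | 1.45 |

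A ratio above 1 means that larotrectinib looks worse than it is. These figures are unweighted. They hold pE at 0.04 and, for power, the hazard ratio at 0.25.

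**Step 4. Set the dates side by side.** The source criterion runs to the present. TRKi access opened in December 2015 through SCOUT and widened in March and September 2019. Protocol 9.9 says there was no overlap. Both can be true only if follow-up of the selected controls ended before a TRKi was available to them. Neither document gives index dates or end of follow-up for the Curie or CWS patients, so this cannot be settled from the text.

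**The case against.** The strongest reply is that the rule may remove nobody. If the statement in Protocol 9.9 is accurate, the bias is nil. The 2000-to-present window describes which sources qualify, not when the selected controls were treated. This stands: the size is unknown and zero is possible.

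A reader might infer that the control arm has been shown to be stripped of its refractory patients, pointing to SAP 7, where only 8 of 42 controls had a second or later line, fewer than anticipated. The documents do not support that. They report no control removed under this rule, and a low second-line count has other explanations. Nor is 8/42 the control failure rate: it omits radiotherapy, mutilating surgery and death. Its closeness to the assumed 0.19, which comes from the literature, is coincidental. It is also not true that everyone excluded is a failure, since some may have had a TRKi at or before baseline.

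Three further points have force:
- The exclusion keeps the secondary endpoints a comparison with care free of TRKi treatment.
- It stops a patient who moved into SCOUT from counting in both arms.
- The likely bias runs against the sponsor's product, in a study already labelled exploratory.

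The first two must be handled in any change. The third does not make the selection valid. The plan calls its primary estimate conservative because of line of therapy (Protocol 9.7.1), which is a different matter.

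**Conclusion.** The defect in the rule is established from the text: as written, control membership can depend on a component of the control's own primary outcome. Its effect is conditional. If one or more controls started a TRKi after first-line chemotherapy, the control failure rate is understated and the primary comparison is probably biased against larotrectinib. The direction is probable rather than certain because the effect after weighting cannot be derived from the documents.

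The illustrated range, from no change up to nine percentage points in control failure probability (0.19 to 0.28), rests on an assumed count of 0 to 5 and on the SAP's planning values, not on observed data. The point deserves correction because the change fits the plan's own endpoint and because reporting one count would show whether it matters. The statement in Protocol 9.9 and the calendar facts in Protocol 7.5.1, 9.2.3.1 and 9.2.4 need to be reconciled in any case.

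**What to change.** 1. Limit the TRKi exclusion, and the investigational-program exclusion beside it, to exposure before or as the index therapy. Without the second change, a control who later entered SCOUT would still be removed. Apply the rule at each analysis's own index line: a control whose second line was a TRKi stays in the primary analysis as an event, but is excluded from the second-line subgroup in SAP 6.2.5.
2. Keep later TRKi starters and count the TRKi start as the subsequent-systemic-treatment event, unless an earlier event occurred.
3. For overall survival, and for times to radiotherapy, mutilating surgery and complete resection, show results both uncensored and censored at TRKi start, stating that this censoring is likely to be informative. Progression-free survival already has a rule for new therapy (SAP 6.3.6, rule 7).
4. Report how many controls the present rule removed and when each started a TRKi, and reconcile Protocol 9.9 with the calendar window.

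**Cost.** Items 1 to 3 need changes of wording and a small re-extraction, which may fall under the data-transfer and authorisation steps in Protocol 9.6.1 and section 10. The main downside is that a control who later entered SCOUT could appear in both arms. If records can be linked, resample by patient in the bootstrap. SCOUT data are pseudonymised, with the linking list held at sites (Protocol 9.6.1), so linkage may not be possible. In that case, add a sensitivity analysis that drops controls whose later TRKi was given in SCOUT or came from an unknown source. That analysis brings back the deletion for those patients, so it should be read beside the main result and not replace it.
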